6.2 Primary Objective

To describe utilization of systemic glucocorticoids (e.g., dexamethasone, prednisolone, methylprednisolone or hydrocortisone) for treatment of COVID-19 in two settings: hospitalized (in hospital care) and ambulatory (any care received outside of hospital) within 90 days following COVID-19 diagnosis. The following variables will be described:

- Prevalent use or naïve (incident) use of systemic glucocorticoid at date of diagnosis of COVID-19
- Concomitant use of other medications (number and type) and invasive/non-invasive respiratory support during follow up
- Type of systemic glucocorticoid received
- Time to systemic glucocorticoid initiation from COVID-19 diagnosis
- Route of administration
- Systemic glucocorticoid daily dose at initiation (treatment index date), cumulative duration, distribution of duration of use and cumulative dose of systemic glucocorticoid received
- For prevalent users: proximity of previous glucocorticoid use to COVID-19 diagnosis (current use (concomitant on date of COVID-19 diagnosis, recent use (between 15-30 days before date of COVID-19 diagnosis) or remote use (use ended more than 30 days before date of COVID-19 diagnosis))

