7.2.2 Patient Selection

7.2.2.1 Inclusion Criteria

Four cohorts will be created based on healthcare setting and type of steroid use. Their eligibility criteria being described below (using Covid-19 catch-all definition Section 7.3.1):

Ambulatory prevalent user

- Have at least 365 days of continuous observation time prior to cohort entry
- Have a glucocorticoid (oral or parenteral) exposure in the 120 days prior to diagnosis date (unrelated to COVID-19 diagnosis)
- Have a positive PCR test for SARS-CoV-2 (labCOVID-19) or a confirmed COVID-19 diagnosis (diagCOVID-19)
- Have no hospitalizations in the 30 days prior to or on index

Ambulatory naive user

- Have at least 365 days of continuous observation time prior to cohort entry
- Have no glucocorticoid (oral or parenteral) exposure in the 120 days prior to index (unrelated to COVID-19 diagnosis)
- Have a positive PCR test for SARS-CoV-2 (labCOVID-19) or a confirmed COVID-19 diagnosis (diagCOVID-19)
- Have no hospitalizations in the 30 days prior to or on index

Hospitalized prevalent user

- Have a glucocorticoid (oral or parenteral) exposure in the 120 days prior to index (unrelated to COVID-19 diagnosis)
- Have a positive PCR test for SARS-CoV-2 (labCOVID-19) or a confirmed COVID-19 diagnosis (diagCOVID-19) (index date)
- Are hospitalized 30 days prior or after diagnosis index date
- Have no intensive services in the 30 days prior to or on index

Hospitalized naïve user

- Have no prior exposures to glucocorticoids in the 120 days prior to index
- Have a positive PCR test for SARS-CoV-2 (labCOVID-19) or a confirmed COVID-19 diagnosis (diagCOVID-19)
- Are hospitalized 30 days prior or after diagnosis index date
- Have no intensive services in the 30 days prior to or on index

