7.2.3 Follow-up

Two index date definitions will be applied as appropriate for each objective.

- Diagnosis index date is defined as a positive PCR test for SARS-CoV-2 (labCOVID-19) or a confirmed COVID-19 diagnosis(diagCOVID-19) whichever is the earliest.
- Treatment index date is defined as start of first systemic glucocorticoid treatment episode specifically for the treatment of COVID-19, irrespective of whether the patient is a prevalent or naïve user.

Follow up for all patients will begin from the index date until they experience the outcome of interest (endpoint, depending on the objective) or until cohort exit (date of censoring). The patients will be followed up for maximum 90 days or until censoring occurs, censoring criteria are:

- death
- patient exit (deregister) from a contributing data provider (GP practice)
- end of the database's data collection
- end of study period (latest data cut-off)

The lookback window for evaluating risk factors, medical history is 365 days and will be applied only to outpatient cohorts.

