7.2.4 Subgroups

The following subgroups will be used to stratify the descriptive tables in Primary objective 1 and secondary objective 1-3. These are a mix of contraindications (e.g. heart failure, myocardial infarction, ischaemic stroke, hypertension, diabetes) and underrepresented groups in clinical trials (e.g. renal

impairment, hepatic impairment) as well as conditions for which glucocorticoids are indicated (COPD and asthma).

Comorbidities

- Cardiovascular diseases¹ (e.g., hypertension, arrhythmia, valve disorders, stroke, acute myocardial infarction)
- Type 2 diabetes mellitus
- Respiratory diseases: asthma, COPD
- Renal impairment
- Hepatic impairment
- Autoimmune diseases (e.g., type 1 diabetes mellitus, rheumatoid arthritis, psoriasis, psoriatic arthritis, multiple sclerosis, systemic lupus erythematosus, Addison's, Graves, Sjogrens, Hashimoto, myasthenia gravis, autoimmune vasculitis, pernicious anaemia, celiac disease, scleroderma, sarcoid, ulcerative colitis, Crohn disease)
- Starting dose of steroids: low dose and high dose (the threshold will be decided based on data distribution)

Speciality of the healthcare practitioner (GPs vs specialists) in databases that record this information

The subgroups are not mutually exclusive, and patients can contribute to more than one subgroup, The above subgroups will be used for descriptive purposes and will not be used for statistical comparisons.

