7.3.2.1 Glucocorticoids

Glucocorticoids used in COVID-19 indication

The primary treatment group of interest is based on exposure to systemic glucocorticoids. The following drugs will be considered as being used for COVID-19 diagnosis:

- Dexamethasone (H02AB02)
- Prednisone (H02AB07)
- Prednisolone (H02AB06)
- Methylprednisolone (H02AB04)
- Hydrocortisone (H02AB09)

Only glucocorticoids which were investigated in clinical trials (13,21) or are recommended by clinical guidelines are included (22–24) to avoid misclassification of steroids used for other conditions. As indication is not captured in the available databases, a glucocorticoid treatment will be considered to have been initiated for COVID-19 treatment if:

For incident users

- The glucocorticoid treatment was initiated between 2 before and 30 days after COVID-19 diagnosis date (21)
- It is one of the five glucocorticoids recommended for COVID-19 as above

For prevalent users

- The glucocorticoid treatment was initiated between 2 before and 30 days after COVID-19 diagnosis date
- It is one of the five glucocorticoids recommended for COVID-19 as above
- The glucocorticoid started after COVID-19 diagnosis differs from the chronically used glucocorticoids OR there is a change in dose or schedule of administration compared to the prevalent use, occurred after COVID-19 diagnosis.

Glucocorticoids for pre-existing conditions

For the prevalent users, any steroid in the ATC class H02 glucocorticoids for systemic use will be considered. A patient is defined as a systemic glucocorticoids prevalent user if it has at least one prior exposure to systemic² glucocorticoids in the 120 days prior to diagnosis index date.

For the description of prevalent users of glucocorticoids, categories of use will be created based on proportion of days covered (PDC) during the lookback period. PDC is calculated as the number of days in period covered by prescriptions divided by number of days in the period.

- PDC > 85% as heavy user
- PDC 50-85% as moderate user
- less than 50% PDC as light user

Another categorization of prevalent glucocorticoids user will be based on how recently in the past the last prescription was observed:

- current use (concomitant on date of COVID-19 diagnosis)
- recent use (between 15-30 days before date of COVID-19 diagnosis)
- remote use (use ended more than 30 days before date of COVID-19 diagnosis)

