7.3.2.3 Operationalization of exposure metrics

Cumulative duration

For glucocorticoids used in COVID-19 indication

Exposure to a treatment will commence on the date of the first qualifying record, subject to satisfying all inclusion criteria listed in section 7.2.2. Each drug exposure record has a start date and inferred end date, which is either explicitly entered or derived from other available information, such as days' supply or refills. Duration of each episode will be calculated as end date minus start date or directly from days' supply variable, whatever available. For each patient, the cumulative duration of use will be calculated as the sum of the duration of treatment episodes.

Table 3 Calculation of duration of use and end of treatment across databases

	IPCI	UK IMRD	Germany DA	Belgium LPD	SIDIAP	France LPD
If days_supply is missing	Use amount and dose extracted from the sig	Use daily dosage along with prescribed quantity	Impute with the most frequent daily dosage or DDD at a therapy level	Use calculated quantity/units_per_day.	Use the quantity, daily dosage and DDD of each drug	Use the quantity and daily dosage of each drug
If still missing	Use the DDD and prescribed quantity	Impute most frequent daily dose at the drug level	-	-	-	-
If still missing	Use the modal duration in the database					

DDD= defined daily dose; sig - the directions ('signetur') on the drug prescription as recorded in the original prescription (and printed on the container) or dispensing record from the physician.

Daily dose

For glucocorticoids used in COVID-19 indication, the prescribed daily dose at initiation of glucocorticoid (treatment index date) will be recorded and categorized in low and high dose. The definition of low dose and high dose will use the cut off defined by WHO in their prospective meta-

analysis from REACT subgroup (16), namely: 15 mg/d of dexamethasone, 400 mg/d of hydrocortisone, and 1 mg/kg/d of methylprednisolone.

The current recommendation is to use 10 mg of dexamethasone for maximum 10 days, administered orally or intravenously. In case glucocorticoids other than dexamethasone are administered, their dose will be converted in prednisolone equivalents as described:

<https://emedicine.medscape.com/article/2172042-overview>

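### Prior use that ended 1–14 days before diagnosis has no recency category, and low/high starting dose is defined by two conflicting rules

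*Protocol*

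**What the plan says.** **Recency.** Protocol 6.2 makes proximity of earlier use a primary-objective variable for prevalent users. The abstract, 6.2 and 7.3.2.1 give the same classes. The first is "current use (concomitant on date of COVID-19 diagnosis"). The second is "recent use (between 15-30 days before date of COVID-19 diagnosis"). The third, remote, is for use that had stopped over 30 days earlier. Section 7.3.2.1 introduces them as depending on when the last prescription was seen, yet words the remote class by when use ended. Prevalent use itself is any systemic exposure in the 120 days before diagnosis (7.2.2.1, 7.3.2.1).

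**Starting dose.** Section 7.2.4 lists low and high starting dose as a subgroup for the tables of the primary objective and secondary objectives 1–3, and says "the threshold will be decided based on data distribution". Section 7.3.2.3 categorises the daily dose at initiation by fixed cut-offs from an external meta-analysis: "15 mg/d of dexamethasone, 400 mg/d of hydrocortisone, and 1 mg/kg/d of methylprednisolone". It then says that doses of glucocorticoids other than dexamethasone are converted to prednisolone equivalents. Section 7.3.2.1 lists five drugs: these three plus prednisone and prednisolone.

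**Two smaller points.** For hospitalised naive users, 7.2.2.1 requires: "Have no prior exposures to glucocorticoids in the 120 days prior to index". The other three cohorts qualify this exposure as unrelated to COVID-19; this one does not. For intensity of earlier use, 7.3.2.1 says "categories of use will be created based on proportion of days covered (PDC) during the lookback period", without giving the length of that period.

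**The concern.** Classes meant to describe every prevalent user should be exhaustive and should not overlap. Here the group closest to current exposure, those who stopped within the two weeks before diagnosis, has nowhere to go. An analyst would have to drop them, widen the current class or widen the recent class, and each choice gives a different table.

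The two dose rules cannot both be followed. One looks at the data before setting the threshold; the other sets it beforehand. Both concern the dose at treatment start, and neither is given precedence. The amendment table dates both additions to 16 November 2020, so neither looks like leftover text. Databases are analysed separately (7.7), so a threshold taken from the data could also differ between them unless the protocol rules that out.

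**Working it through.** The protocol gives no figure to reproduce here, so the check applies the rules as written.

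**Step 1: recency by end of use.** Each day from 0 to 120 before diagnosis was set against the three classes.

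| Last use ended (days before diagnosis) | Class | Days |
|---|---|---|
| Use covers the diagnosis date | current | – |
| 1–14 | none | 14 |
| 15–30 | recent | 16 |
| 31–120 | remote | 90 |

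14 + 16 + 90 = 120. No day falls in two classes. The gap is 14/120 = 11.7% of lookback days.

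**Step 2: does another rule close the gap?** Section 7.3.2.3 allows a 7-day persistence window between records, but for outcome assessment. Applied to recency anyway, it would still leave days 8–14 open. The 14 days in the sensitivity analysis of 7.7.8 is a duration of use and does not define recency.

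**Step 3: the mixed basis.** Suppose the recent class is judged by prescription date, and the current and remote classes by end of use. Length of supply is an assumption here.

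- 5-day supply: prescriptions issued on days 6–14 and 31–35 have no class, 9 + 5 = 14 days.
- 30-day supply: days 31–60 have no class (30 days), and days 15–30 are both current and recent (16 days).

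The basis therefore changes both where the holes lie and whether classes overlap.

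**Step 4: dose.** Section 7.3.2.3 states cut-offs for 3 of the 5 drugs in 7.3.2.1. Prednisone and prednisolone have none. No cut-off is stated on the prednisolone-equivalent scale, and the conversion sentence leaves dexamethasone out, so the step from converted dose to low or high is not given.

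**Step 5: starts 1–2 days before diagnosis.** Section 7.3.2.1 counts a listed glucocorticoid started up to 2 days before diagnosis as COVID-19 treatment. Take a hospital patient with no other earlier use. Under 7.2.2.1 the start is related to COVID-19, so the patient is not a prevalent user; it is also an exposure in the previous 120 days, so the patient is not naive. The patient fits neither hospital cohort.

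**Step 6: PDC denominator.** Prevalent use is judged over 120 days. Section 7.2.3 states "The lookback window for evaluating risk factors, medical history is 365 days", and restricts it to outpatient cohorts. For a patient covered throughout the last 120 days and not before:

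- over 120 days: 120/120 = 100%, heavy user (above 85%);
- over 365 days: 120/365 = 32.9%, light user (below 50%).

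The text should say which denominator applies.

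**The case against.** The best defence is that these are short wording gaps in a descriptive study. Results are shown separately by country and database (7.7), the subgroups are not used for statistical comparisons (7.2.4), and pooling is by treatment group (7.7.7). That is right: no planned test or pooled estimate depends on the recency classes or the dose split. It limits the harm but does not supply the missing class or choose between the dose rules.

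A reader might infer more than the documents support:

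- **That the primary-objective tables as a whole cannot be filled.** Drug type, route, time to initiation, duration, cumulative dose and concomitant treatment do not depend on these classes. The daily dose is also recorded as such, apart from its category.
- **That 11.7% of patients are lost.** It is a share of days. It would be a share of non-current prevalent users only if their end dates were spread evenly over the 120 days, which nothing in the protocol supports. A prescription issued 1–14 days before diagnosis whose supply reaches that date is current.
- **That PDC is computed over 365 days.** Section 7.2.3 ties that window to risk factors and medical history. The 33% is one reading of an unstated denominator.
- **That the mg/kg cut-off cannot be applied for want of weight.** Weight is not listed separately in 7.3.5, but Appendix 1, section 5.7, includes a body-weight concept. Its completeness is unknown.
- **That every prednisone or prednisolone starter is unclassifiable.** The conversion might provide a common scale, but the source it links to is not available here. The defect is that the link to a category is not stated.

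On the hospital cohorts, the unqualified prevalent-user definition in 7.3.2.1 stands under the heading for pre-existing conditions, and the rule for incident users there already allows a start 2 days before diagnosis. The intent is therefore clear, and what is missing is one exception in 7.2.2.1.

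**Conclusion.** The point holds for two rules. The recency classes leave use that ended 1–14 days before diagnosis unassigned in all three places where they are defined, and they mix two bases. The low/high starting dose has two incompatible definitions, the fixed one with stated cut-offs for three of five drugs. No other section cures either defect.

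The gap is 14 of 120 lookback days on an end-of-use basis; how many patients it holds cannot be derived from the protocol. The effect is confined to the recency breakdown and the low/high dose strata, with a minor effect on the few hospital patients in Step 5. The PDC classes themselves have no gap; only their denominator needs stating. These are not details left for an analysis plan, because the protocol states the rules and states them incompletely or in conflict. They should be repaired before extraction.

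**What to change.** 1. **Recency (abstract, 6.2, 7.3.2.1).** Make the classes exhaustive and state end of use as the single basis. Examples are recent use defined as ended 1–30 days before diagnosis, or a separate 1–14 day class. Either leaves 0 of 120 days unassigned.
2. **Starting dose (7.2.4, 7.3.2.3).** Reconcile the two sections to one rule, fixed before the data are seen, covering all five drugs and applied identically in every database. State how a converted dose leads to a category. The choice of cut-off is for the protocol's authors.
3. **Hospitalised naive users (7.2.2.1).** Add the exception for exposure related to COVID-19 that the other cohorts carry. Tie it to the listed drugs started 1–2 days before diagnosis rather than dropping those two days for every drug. Otherwise a patient whose only earlier steroid is another drug of ATC class H02, started in those days, would wrongly become naive.
4. **PDC (7.3.2.1).** State that the denominator is the 120-day window that defines prevalent use.

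The cost is a few sentences and matching edits to the phenotype definitions. No new data are needed.

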7.3.2.2 Other COVID-19 treatments

Additional distinct treatment cohorts will be created based on use of other drugs that might be used as treatment of COVID-19 according to various guidelines. Patients will be considered exposed to other pharmacotherapeutic treatments for COVID-19 if available prescription data are available and if the drugs are in the list below.

- a) antiviral therapy (AV);
- b) antibiotic therapy (AB)
- c) immune-based therapy (IB)
- d) antithrombotic therapy (AT)
- e) anti-hypertensives (AH)
- f) statins (S);
- g) anti-diabetics (AD);

² Systemic effects of inhaled and topical use of glucocorticoids is considered low and therefore use will not be considered for this study

These treatments were identified and classified through systematic review of CDC treatment guidelines, clinicaltrials.gov, or clinical guidelines, as part of another OHDSI project. (25) The full list of products is available in Appendix 3.

7.3.2.3 Operationalization of exposure metrics

Cumulative duration

For glucocorticoids used in COVID-19 indication

Exposure to a treatment will commence on the date of the first qualifying record, subject to satisfying all inclusion criteria listed in section 7.2.2. Each drug exposure record has a start date and inferred end date, which is either explicitly entered or derived from other available information, such as days' supply or refills. Duration of each episode will be calculated as end date minus start date or directly from days' supply variable, whatever available. For each patient, the cumulative duration of use will be calculated as the sum of the duration of treatment episodes.

Table 3 Calculation of duration of use and end of treatment across databases

	IPCI	UK IMRD	Germany DA	Belgium LPD	SIDIAP	France LPD
If days_supply is missing	Use amount and dose extracted from the sig	Use daily dosage along with prescribed quantity	Impute with the most frequent daily dosage or DDD at a therapy level	Use calculated quantity/units_per_day.	Use the quantity, daily dosage and DDD of each drug	Use the quantity and daily dosage of each drug
If still missing	Use the DDD and prescribed quantity	Impute most frequent daily dose at the drug level	-	-	-	-
If still missing	Use the modal duration in the database					

DDD= defined daily dose; sig - the directions ('signetur') on the drug prescription as recorded in the original prescription (and printed on the container) or dispensing record from the physician.

Daily dose

For glucocorticoids used in COVID-19 indication, the prescribed daily dose at initiation of glucocorticoid (treatment index date) will be recorded and categorized in low and high dose. The definition of low dose and high dose will use the cut off defined by WHO in their prospective meta-

analysis from REACT subgroup (16), namely: 15 mg/d of dexamethasone, 400 mg/d of hydrocortisone, and 1 mg/kg/d of methylprednisolone.

The current recommendation is to use 10 mg of dexamethasone for maximum 10 days, administered orally or intravenously. In case glucocorticoids other than dexamethasone are administered, their dose will be converted in prednisolone equivalents as described:

<https://emedicine.medscape.com/article/2172042-overview>

Steroids often have adjusted dose regimens such that drug may be slowly increased or decreased over time and short acute treatment episodes are also possible. Such changes in dose over time will not be examined, however total cumulative dose will be examined in relation to outcomes of interest (see below).

Cumulative dose

For glucocorticoids used in COVID-19 indication, orally administered, if quantity is available, the formula to calculate the cumulative exposure in mg is described below:

$$Cumulative\ dose_{solid}[mg] = \sum_{all\ exposures} quantity \times amount_value [mg]$$

If the **quantity is missing**, the number of units per day for solid formulations are extracted. The cumulative exposure in mg can then be calculated using the following formula:

$$Cumulative\ dose_{solid}[mg] = \sum_{exposures} units\ per\ day \times amount_value [mg] \times duration$$

For intravenous administration (bolus administration), the dose administered each time will be counted.

$$Cumulative\ dose\ intravenous [mg] = \sum_{all\ exposures} amount_value [mg]$$

Exposure groups for incidence calculation (secondary objective 2 and 3)

For the incidence rates calculation, an on-treatment exposure will be considered with mutually exclusive groups to allow calculation of incidence rates.

Each person will be classified as belonging to one of the following mutually exclusive exposure groups at treatment index date following COVID-19 diagnosis:

- Use of systemic glucocorticoids without other treatments for COVID-19 (drug and respiratory support)
- Use of systemic glucocorticoids plus other treatments for COVID-19 (drug and respiratory support)
- Only other treatments and respiratory support with no systemic glucocorticoids

- No specific treatments for COVID-19 infection (other concomitant treatments for indications other than for COVID-19 are allowed)

A single prescription would be enough to consider the patient as exposed. See section 7.3.2.1 for description of 'other treatment for COVID-19' that are included.

Only the first episode of exposure will be considered, patients being censored when they switch to another treatment (including switch to another glucocorticoid) or when follow up ends. Duration of follow-up for each treatment cohort will be summarized and will constitute the denominator for calculation of effect estimates. A persistence window of 7 days between drug utilization records for each study drug will be allowed considered as continuous exposure for the outcome's assessment.

In case that more than 70% of the patients are censored, a sensitivity approach will be applied for objectives 2 and 3 (see Section 7.7.8).

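### Section 7.3.2.3 relates total cumulative glucocorticoid dose, which builds up after the treatment index date, to outcomes; where dose accrues by repeated administration, early death forces a low total

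*Protocol*

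**What the plan says.** All references are to the Protocol.

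- **Section 7.3.2.3** sets aside titration and tapering ("Such changes in dose over time will not be examined") and continues: "however total cumulative dose will be examined in relation to outcomes of interest". The formulas that follow sum over exposures. Oral dose is quantity times strength or, if quantity is missing, units per day times strength times duration. For intravenous use "the dose administered each time will be counted". No formula stops the sum at the event, at a fixed day or at a lag.
- **Section 7.2.3** fixes time zero: "Treatment index date is defined as start of first systemic glucocorticoid treatment episode specifically for the treatment of COVID-19". It then says: "Follow up for all patients will begin from the index date until they experience the outcome of interest". The maximum is 90 days, and death is listed as a censoring criterion.
- **Section 7.3.2.3**, on incidence calculation, adds: "Only the first episode of exposure will be considered".
- **Section 7.2.4** lists a dose measure that is fixed at time zero: "Starting dose of steroids: low dose and high dose". It applies to secondary objectives 1 to 3.
- **Section 7.7.2** uses cumulative dose only to describe prescribing. Sections 7.7.4 and 7.7.5 give crude rates and Cox models without mentioning cumulative dose, a time-dependent covariate or a landmark. The limitations in section 7.9 do not mention the issue.

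**The concern.** A total that is known only at the end of treatment is to be set against events counted from the start of treatment. If each administration adds to the total, the total depends on how long the patient stays alive to receive it. At 10 mg a day, a patient who dies after three daily doses has a total of 30 mg, while a survivor who completes ten days has 100 mg, whatever the drug does. Classifying patients by that total uses future exposure to define groups at time zero.

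For non-fatal events the problem takes another form. If all exposures are summed as the formulas say, the total can include dose given after the event. An event may be followed by shorter or longer treatment, so the direction of that bias is not fixed.

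Section 5.0 names dose among the unanswered questions, so readers are likely to use a table of mortality by total dose.

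**Working it through.** The plan states no figure for this analysis, so there is nothing to reproduce. The artefact can be sized by assuming that dose has no effect on death.

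**Inputs**

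| Input | Value | Source |
|---|---|---|
| 30-day death risk | 26% | Hospital case fatality in section 5.0 (given there as over 26%); the 30-day period is assumed |
| Hazard | constant | assumption |
| Dose per day alive and on course | 10 mg | Section 7.3.2.3, for scale only; the risk ratio depends on days, not mg |
| Planned course | half 5 days, half 10 days, unrelated to prognosis | assumption |

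**Closed-form illustration**

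1. Daily hazard: h = −ln(1 − 0.26)/30 = −ln(0.74)/30 = 0.01004.
2. Death before a sixth daily dose: 1 − exp(−5h) = 0.0489.
3. The group with a total of 50 mg or less contains all 5-day patients and the 10-day patients who die before the sixth dose. Its mortality is (0.5 × 0.26 + 0.5 × 0.0489)/(0.5 + 0.5 × 0.0489) = 29.5%.
4. The group above 50 mg contains the 10-day patients who live to the sixth dose. Its mortality is (0.26 − 0.0489)/(1 − 0.0489) = 22.2%.
5. Spurious risk ratio: 22.2/29.5 = 0.75, although the true ratio is 1.
6. Extreme case, with every patient planned for 10 days: all patients with an incomplete total have died (100%). Those who receive the tenth dose have 21 of the 30 days left, and their mortality is 1 − exp(−21h) = 19.0%.

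**Simulation under no dose effect**

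There were 20,000 patients with a 26% 30-day death risk and 10 mg counted for each day alive on course. Course length was uniform over 5–10 or 1–10 days (assumed). The hazard was constant or front-loaded (Weibull shape 0.7, assumed). The final total entered a Cox model as a fixed covariate.

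| Course, hazard | Mean total, died vs survived (mg) | HR per 10 mg | HR at or above vs below median total |
|---|---|---|---|
| 5–10 d, constant | 65.5 vs 74.9 | 0.72 | 0.54 |
| 5–10 d, front-loaded | 57.5 vs 75.0 | 0.55 | 0.38 |
| 1–10 d, constant | 49.3 vs 55.3 | 0.93 | 0.71 |
| 1–10 d, front-loaded | 43.0 vs 55.0 | 0.87 | 0.51 |

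At 3% (40,000 patients) and 37% death risk, the high-versus-low HR ranged from 0.39 to 0.74.

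**Same data at 26%, with dose handled correctly (HR per 10 mg)**

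- time-updated cumulative dose: 0.991 to 1.003
- landmark at day 10: 0.984 to 1.007
- planned amount fixed at index: 0.994 to 1.000

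These are null apart from simulation noise, so the apparent protection comes from how dose is handled. The third line also shows the limit of the point: if the whole quantity is fixed at index, the artefact disappears.

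**The case against.** The strongest reply is that the protocol never specifies this analysis. The sentence sits in the section on exposure metrics, the text it points to only computes milligrams, and sections 7.7.4 and 7.7.5 give cumulative dose no outcome model. Declining to examine dose changes may refer only to tapering patterns, and a SAP could still choose a time-updated form. This is partly right: the issue rests on one clause. But that clause selects the whole-course total for use against outcomes, and its formulas have no stopping rule. A SAP that followed it literally would inherit the fault. The first-episode rule does not help, because dose accrues within the first episode.

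Four further limits stand.

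- **Prescribed quantity.** The main oral formula counts what was prescribed. If one prescription covers the course, an early death and a survivor have the same total. Seven of the eight databases are ambulatory sources with mainly prescription-based drug data. The hospital database has around 2,000 of 153,759 patients (section 7.5), about 1.3%. Three databases record no vital status at all (section 7.9.2).
- **Non-fatal events.** A reader might infer that any early event forces a low total. The text does not support that: the total is low only if dosing stops being counted at the event, and the formulas do not say so.
- **Net direction.** A reader might also infer that the published estimate will favour higher dose. Section 7.9.1 rates confounding by severity as high, and it could push the other way.
- **Scope.** Section 6.3 excludes comparisons between treatments and between treated and untreated patients. Dose relations among treated patients are not excluded.

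Outcomes by starting dose are already planned in section 7.2.4, so that part of the remedy exists.

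**Conclusion.** The point holds in a limited form. As worded, section 7.3.2.3 relates outcomes to a dose total that accrues after time zero. For death, where dose builds up by administration or refill, this alone produces an apparent benefit of a higher total: a risk ratio of about 0.75 in the simple illustration and high-versus-low hazard ratios of 0.38 to 0.71 in the simulations at 26% mortality. These sizes rest on assumed course lengths and hazard shapes, on a hospital case fatality and on daily accrual. They do not carry over to ambulatory patients whose single prescription fixes the quantity at index, where the bias is weak or absent.

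For non-fatal events, dose after the event may be counted and the direction is uncertain. The documents do not support saying that every dose table in every database will be biased, or that the net result will favour higher dose. The change should be made because the clause is faulty as a rule, but it concerns a secondary analysis and leaves the primary utilisation objective intact.

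**What to change.** In section 7.3.2.3, replace the clause on total cumulative dose and outcomes with wording such as:

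*Total cumulative dose is a descriptive utilisation measure for the primary objective. Outcomes will be described by starting daily dose at the treatment index date (section 7.2.4). Any analysis of cumulative dose against outcomes will treat it as a time-updated quantity: person-time and events are assigned to the dose received up to that day, and dose after the event is ignored.*

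The cost is one changed sentence. If the time-updated analysis is kept, person-time must be split by accrued dose, which needs a little more programming. If it is dropped, there is no further work. No clinical rule changes.
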